Section 8.3.6.1 Injection/Infusion Site Reactions	Removed Infusion site reactions from section. Added/deleted text as follows: Deleted text in strikethrough, new text in bold . Antibodies have been associated with injection/infusion reactions, with onset typically during or shortly after completion of the injection/infusion. For this reason, participants will be carefully observed during each injection/infusion. Injection/infusion site reactions are defined as AEs localized to the site of IV or SC route of study drug administration, occurring at any time during study participation that are assessed by the Investigator to be related to study drug. Injection site reactions (ISRs) are defined as AEs localized to the site of study drug administration that occur at any time during study participation that are assessed by the Investigator as possibly, probably, or definitely related to study drug. AE intensity reporting procedures are outlined in Section 10.3.4. Injection site reactions may occur at any timepoint after study drug administration. There is no additional laboratory testing required for ISRs. The Investigator is responsible for monitoring for ISRs in patients throughout the duration of the study. As part of the study-required physical examinations, Investigators should evaluate injection sites for signs of reaction(s).	To clarify descriptions of and symptoms associated with the severity of injection site reactions and to provide cross reference to section of protocol describing reporting of AEs and SAEs.

Section	Description of Change	Brief Rationale and/or Clarification
Section 8.3.6.2 Injection/Infusion- associated Reactions	Removed Infusion site reactions from section. Removed reference to IV administration. Added following sentence as final sentence in the section: AE intensity reporting procedures are outlined in Section 10.3.4.	To clarify for this study, as drug will be administered SC only, and to provide cross reference to section of protocol describing reporting of AEs and SAEs.
Section 8.6 Pharmacodynamics	Whole blood samples will be collected for measurement of PLP/PL, PA , and PPi.	Addition of PA to PLP/PL and PPi
Section 10.2 Clinical Laboratory Tests	Calcium, calcium/creatinine have been removed from routine urinanalysis	Calcium and calcium/creatinine are not part of a routine urinalysis. However, they assessed via a separate collection, and the table has been updated for clarity.

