2.3.1. Risk Assessment

Potential risks of study participation include:

- Injection/infusion site reactions (ISRs)
- Injection/infusion associated reactions (including hypersensitivity)
- Formation of anti-ALXN1850 antibodies
- Ectopic calcifications

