10.2. Clinical Laboratory Tests

- The clinical safety tests detailed in Table 7 will be performed by a local laboratory or by Alexion, as indicated.
- Protocol-specific requirements for inclusion or exclusion of participants are detailed in Section 5.
- Additional tests may be performed at any time during the study as determined necessary by the Investigator or required by local regulations.
- The results of each test must be entered in the eCRF.
- Pregnancy testing: Women of childbearing potential should only be enrolled after a negative serum pregnancy test result at Screening. Urine pregnancy testing will be performed for women of childbearing potential at all subsequent timepoints specified in the SoA (Section 1.3). Additional pregnancy tests may also be performed at any time at the Investigator's discretion.

Laboratory Assessments	Parameters			
Hematology	Red blood cell count Hematocrit	Red blood cell indices Mean corpuscular vol Mean corpuscular hen %Reticulocytes Glycated hemoglobin	ume noglobin	White blood cell count with differential: Neutrophils Lymphocytes Monocytes Eosinophils Basophils Platelet count
Clinical chemistry ^b	Blood urea nitrogen Potassium Creatinine Sodium Chloride Glucose Total carbon dioxide	Aspartate aminotransf /serum glutamic-oxale transaminase Gamma glutamyltrans Alanine aminotransfer glutamic-pyruvic tran Alkaline phosphatase	oacetic sferase rase /serum saminase	Total and direct bilirubin Indirect bilirubin Total protein Albumin Calcium ^c Phosphate Magnesium
Coagulation	Prothrombin time	Partial thromboplastin	n time	International normalized ratio
Other safety laboratory tests	Parathyroid hormone, int 25-OH Vitamin D Antidrug antibodies (Ale Neutralizing antibodies (ca xion) re Alexion) Tr C: Ig He	ise of an acut action: ryptase (Alex 5b-9 (Alexion) E (Alexion)	
Other urine tests	Routine urinalysis: Speci urobilinogen, nitrite, eryt Microscopic examination menstruating] are abnorn	hrocytes, leukocyte este n (if any leukocytes, trac	erase (by dips	stick)

 Table 7:
 Protocol-Required Safety Laboratory Assessments

Laboratory Assessments	Parameters
	Further urinalysis for calcium, phosphorus, creatinine and calcium/creatinine Urine pregnancy tests (after Screening, for women of childbearing potential)
Other screening tests	Alcohol test
	Urine drug screen (to include amphetamines; barbiturates; benzodiazepines; cocaine; opiates; phencyclidine; methamphetamine; 3,4 methylenedioxy-methamphetamine; and methadone)

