eCRF	electronic case report form
HIV	human immunodeficiency virus
HPP	hypophosphatasia
ICF	informed consent form
IgG	immunoglobulin G
IQR	interquartile range
IV	Intravenous(ly)

MedDRA	Medical Dictionary for Regulatory Activities
n	number of non-missing values
N	number of participants
NAb	neutralizing antibody
P1NP	N-terminal propeptide of type I procollagen
PA	pyridoxic acid
PD	pharmacodynamic(s)
PEA	phosphoethanolamine
PK	pharmacokinetic(s)
PL	pyridoxal
PLP	pyridoxal-5'-phosphate
PPi	inorganic pyrophosphate
PT	preferred term
PTH	parathyroid hormone
Q1	quartile 1
Q3	quartile 3
QTcF	QT interval corrected for heart rate using Fridericia's formula
R	subcutaneous accumulation ratio
Rsq	the coefficient of determination
SAE	serious adverse event
SAP	statistical analysis plan
SC	subcutaneous(ly)
SD	standard deviation
SOC	system organ class
SRC	Safety Review Committee
t _{1/2}	apparent terminal elimination half-life
TEAE	treatment-emergent adverse event
TESAE	treatment-emergent serious adverse event
TNSALP	tissue-nonspecific alkaline phosphatase
T _{max}	time of maximum observed concentration
V _d	volume of distribution during the terminal phase
V _d /F	apparent volume of distribution during the terminal phase
%AUC _{extrap}	percentage of AUC _{inf} due to extrapolation
%CV	percent coefficient of variation
λ_{z}	terminal phase elimination rate constant

1. Introduction

Hypophosphatasia (HPP) is a rare, inherited, metabolic disease caused by deficient activity of the tissue non-specific isoenzyme of alkaline phosphatase, typically due to loss-of-function mutation(s) in the *ALPL* gene. ALXN1850 is an investigational enzyme replacement therapy that addresses the underlying cause of HPP by replacing the defective enzyme, thus reversing the mineralization defects of the skeleton and improving systemic manifestations of HPP.

The purpose of this statistical analysis plan (SAP) is to define the planned statistical analysis of the study data consistent with the study objectives. This SAP is written based on protocol ALXN1850-HPP-101, version Amendment 5, dated 11 Mar 2022. Any deviations/changes from the planned analyses described in this SAP will be identified, with justification, in the appropriate section of the clinical study report.

2. Objectives and Endpoints

The study objectives and corresponding endpoints are presented in Table 1.

Table 1: Objectives and Endpoints

Objective	Endpoints
Primary	

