9.2. Clinical Laboratory Evaluations

The following laboratory tests will be performed:

- Hematology: red blood cell count, hematocrit, red blood cell indices (mean corpuscular volume, mean corpuscular hemoglobin, %reticulocytes, and glycated hemoglobin), and white blood cell count with differential (neutrophils, lymphocytes, monocytes, eosinophils, basophils, and platelet count)
- Chemistry: blood urea nitrogen, potassium, creatinine, sodium, chloride, glucose
 (fasting), total carbon dioxide, aspartate aminotransferase/serum glutamic-oxaloacetic
 transaminase, gamma glutamyl transferase, alanine aminotransferase/serum
 glutamic-pyruvic transaminase, ALP (screening only), total and direct bilirubin, indirect
 bilirubin, total protein, albumin, calcium (including ionized calcium), phosphate, and
 magnesium
- Coagulation: prothrombin time, partial thromboplastin time, and international normalized ratio
- Routine urinalysis (by dipstick): specific gravity, pH, glucose, protein, blood, ketones, bilirubin, urobilinogen, nitrite, erythrocytes, calcium, calcium/creatinine, and leukocyte esterase; microscopic examination (if any leukocytes, trace protein, nitrites, and blood [if not menstruating] are abnormal)

Chemistry, hematology, coagulation, and urinalysis will be performed at below timepoint (glycated hemoglobin HbA1c will only be required at screening):

First participant within each cohort	Subsequent participants within each cohort
Screening	Screening
Day -1	Day -1
Day 2 (24 hours post IV dose)	Day 2 (24 hours post IV dose)
Day 8 (1 week post IV dose)	Day 7 (1 week post IV dose)
Day 14 (2 weeks post IV dose)	
Day 16 (24 hours post SC dose 1)	Day 9 (24 hours post SC dose 1)
Day 21 (1 week post SC dose 1)	Day 14 (1 week post SC dose 1)
Day 23 (24 hours post SC dose 2)	Day 16 (24 hours post SC dose 2)
Day 28 (1 week post SC dose 2)	Day 21 (1 week post SC dose 2)
Day 30 (24 hours post SC dose 3)	Day 23 (24 hours post SC dose 3)
Day 36 (1 week post SC dose 3)	Day 29 (1 week post SC dose 3)
Day 65/EoT (6 weeks post SC dose 3)	Day 57/EoT (5 weeks post SC dose 3)

Chemistry laboratory tests at screening must include ALP and PLP.

Relative time to dose will be presented for summary statistics which includes: baseline, 24 hours post IV dose, 1 week post IV dose, 2 weeks post IV dose, 24 hours post SC dose 1, 1 week post SC dose 1, 24 hours post SC dose 2, 1 week post SC dose 2, 24 hours post SC dose 3, and 1 week post SC dose 3.

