9.7. Renal Ultrasound

A renal ultrasound will be performed at the Screening and EoT.

Renal ultrasound results will be presented in a data listing.

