9.9. Other Safety Data

The following other safety assessments will be performed:

- Other safety laboratory tests: intact 25-hydroxy (25-OH) Vitamin D; the following tests are to be conducted in case of an acute injection-associated reaction: tryptase (Alexion), terminal complement complex C5b-9 (Alexion), IgE (Alexion), hematology, chemistry, and urinalysis panels
- Urine electrolyte: urine for calcium, urine for phosphorus, and urine for creatinine
- Follicle stimulating hormone (FSH): confirmation of post-menopausal state

- Human immunodeficiency virus (HIV)-1 and HIV-2 antibodies, hepatitis B surface antigen (HbsAg), anti-hepatitis B core antigen immunoglobulin G (IgG) + immunoglobulin M (if IgG positive) and hepatitis C virus antibodies (anti-hepatitis C virus)
- Serum or urine human chorionic gonadotropin (bHCG) pregnancy test: as needed for women of childbearing potential
- Cross-reactive immunological material assay

Urine for calcium, phosphorus, and creatinine as well as optional phosphoethanolamine (PEA), samples will be collected on Day -1, Day 2, Day 3, Day 8, Day 16, Day 17, Day 23, Day 30, Day 31, and Day 36 for first participant within each cohort, and on Day -1, Day 2, Day 3, Day 9, Day 10, Day 16, Day 23, Day 24, and Day 29 for subsequent participants within each cohort. Optional PEA samples will additionally be collected at screening and Day 65 for first participants and at screening and day 57 for subsequent participants.

Pregnancy test will be performed at screening, Day -1, Day 14, Day 21, and Day 28 for first participant within each cohort, and at screening, Day -1, Day 7, Day 14, Day 21, Day 29, Day 43, Day 57, and Day 78/ED/EoS for subsequent participants within each cohort. A highly sensitive serum bHCG will be performed at Screening and on Day -1; urine tests will be performed during subsequent visits.

Hepatitis B and C, HIV, FSH, and 25-OH vitamin D will be performed at Screening.

Cross-reactive immunological material assay will be performed on Day 1.

Other laboratory tests (including hepatitis B and C, HIV, FSH, and 25-OH vitamin D, urine for calcium, phosphorus, PEA, and creatinine, and pregnancy) will be presented in a separate data listing.

Cross-reactive immunological material assay will be listed in a data listing.

10. Pharmacodynamic Analysis

All PD analyses will be performed on the PD Set and will be summarized by relative time to dose.

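### SAP 9.2 files urine calcium and calcium/creatinine under dipstick urinalysis, and SAP 9.9 only lists the separate urine collection, short of the summary protocol 9.4.2 calls for

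*SAP*

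**What the plan says.** **Protocol.** Table 7 (Section 10.2) separates the dipstick urinalysis from a second line, "Further urinalysis for calcium, phosphorus, creatinine and calcium/creatinine". The Schedules of Activities (Tables 1 and 2) likewise give urinalysis and the urine calcium, phosphorus and creatinine collection separate rows on different days. The Amendment 5 summary of changes gives the reason: "Calcium and calcium/creatinine are not part of a routine urinalysis". Section 9.4.2 says that changes from baseline in the laboratory tests shown in Table 7 are to be summarized for each cohort by visit. Section 2.3.1 names four potential risks, one of which is "Ectopic calcifications".

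**SAP.** The Introduction states: "This SAP is written based on protocol ALXN1850-HPP-101, version Amendment 5". Section 9.2 nevertheless has, within the dipstick panel, "nitrite, erythrocytes, calcium, calcium/creatinine, and leukocyte esterase". It promises summary statistics, change from baseline and shift tables for urinalysis. Section 9.9 describes the separate collection as "Urine electrolyte: urine for calcium, urine for phosphorus, and urine for creatinine", with no ratio, and its only output is this: "urine for calcium, phosphorus, PEA, and creatinine, and pregnancy) will be presented in a separate data listing".

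**The concern.** The SAP gives two instructions for the same analytes. Section 9.2 promises tables, but under a panel and visit schedule that are not the ones on which these results are collected. Section 9.9 has the right collection and the right days, but produces no summary and no ratio. A programmer following 9.9 delivers a listing. A programmer following 9.2 has to decide alone whether to map the separate collection into the urinalysis tables, and what to do with days that those tables do not contain.

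At stake is a repeated urinary measure relevant to a named risk. According to the amendment history, calcium was added to the urine test in Amendment 1, after a regulator's suggestion about monitoring ectopic calcification. Amendment 4 clarified the Day -1 sample so that later changes could be judged against a baseline. Without a change-from-baseline table by cohort, a dose-related drift in urinary calcium has to be found by reading a listing.

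**Working it through.** The documents state no figure to reproduce. The check compares the two SAP schedules day by day and counts what the 9.2 tables could hold.

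**Inputs.** Urinalysis days are from SAP 9.2 and urine collection days from SAP 9.9. Planned enrollment is approximately 15, with about 5 per cohort in 3 cohorts (protocol Synopsis). Each cohort has one first participant, so there are 3 first and 15 − 3 = 12 subsequent participants.

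| | First participant | Subsequent participant |
|---|---|---|
| Urinalysis (SAP 9.2) | Screening, -1, 2, 8, 14, 16, 21, 23, 28, 30, 36, 65 | Screening, -1, 2, 7, 9, 14, 16, 21, 23, 29, 57 |
| Urine collection (SAP 9.9) | -1, 2, 3, 8, 16, 17, 23, 30, 31, 36 | -1, 2, 3, 9, 10, 16, 23, 24, 29 |
| Post-baseline collections | 9 | 8 |
| Of these, on a 9.2 day | 6 (2, 8, 16, 23, 30, 36) | 5 (2, 9, 16, 23, 29) |
| Of these, not on a 9.2 day | 3 (3, 17, 31) | 3 (3, 10, 24) |

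**Totals.**
- Planned post-baseline collections: 3 × 9 + 12 × 8 = 27 + 96 = 123.
- On a 9.2 urinalysis day: 3 × 6 + 12 × 5 = 18 + 60 = 78, and 78/123 = 63%.
- Not on a 9.2 day: 3 × 3 + 12 × 3 = 9 + 36 = 45, and 45/123 = 37%.

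**What the 45 are.** Days 3, 17 and 31 for first participants, and 3, 10 and 24 for subsequent participants, are the 48-hour samples after the IV dose, SC dose 1 and SC dose 3. The relative times that SAP 9.2 lists for summary are baseline, 24 hours, 1 week and (after the IV dose only) 2 weeks. None is 48 hours. The shortfall is therefore every 48-hour sample.

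**Sensitivity to enrollment.** The missed share is 3/9 = 33% for a first participant and 3/8 = 37.5% for a subsequent one, so any mix lies between these. With only 3 per cohort (3 first, 6 subsequent) it is 27 of 75: 3 × 3 + 6 × 3 = 27, 3 × 9 + 6 × 8 = 75, and 27/75 = 36%.

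**Side by side.** Under 9.9 as written, none of the 123 is summarized. Under the most generous reading of 9.2, 78 are. Neither reading gives the full change-from-baseline summary by visit.

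**The case against.** The strongest defense is that SAP 9.2 names both analytes and promises urinalysis summaries, so the intention to summarize is there and only the dipstick label is wrong. Table 7 also keeps both kinds of urinalysis in one row of urine tests. This has force: a reader should not infer that the 9.2 tables must be empty, or that all 123 collections necessarily go unsummarized, because 78 fall on 9.2 days. It does not remove the conflict with 9.9 or recover the 48-hour samples.

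A reader might also infer that ectopic calcification gets no summary at all, or that urine calcium is its only quantitative repeated marker. The documents do not support either. SAP 9.1 tabulates treatment-emergent events by system organ class and preferred term, and protocol 10.3.1 makes clinically significant laboratory or imaging abnormalities adverse events. SAP 9.2 summarizes blood calcium, ionized calcium and phosphate, with shift tables. What is missing is a dedicated summary. The adverse event route also captures only findings that the investigator judges clinically significant.

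Protocol 9.4.2 cannot sensibly be read as covering every Table 7 row, since drug screens, HIV serology and pregnancy tests have no meaningful change from baseline. That limit does not excuse the urine tests, which are numeric, repeated and have a planned baseline.

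Finally, listings are readable with about five people per cohort. That is true, but the SAP summarizes its chemistry, hematology, coagulation and urinalysis panels at the same sample size.

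**Conclusion.** The point stands as an inconsistency between SAP and protocol that should be corrected. SAP 9.2 assigns urine calcium and calcium/creatinine to the wrong panel. SAP 9.9 only lists the collection that holds them and omits the ratio, which falls short of protocol 9.4.2. On the reading most favorable to the SAP, 45 of 123 planned post-baseline collections (37%) remain outside any summary, all of them 48-hour samples. The counts assume 3 first and 12 subsequent participants attending every scheduled collection.

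The consequence is limited. The study is descriptive, and the primary endpoint, incidence of treatment-emergent adverse events, is untouched.

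It may be tempting to treat the listing-only handling of the eye examination and renal ultrasound as part of the same error. For ultrasound the SAP says "Renal ultrasound results will be presented in a data listing", and the eye examination is handled likewise. Protocol 9.4.2 asks for no summary of either, so these are not contradictions and do not follow from the misplaced urine tests.

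**What to change.** 1. In SAP 9.2, delete calcium and calcium/creatinine from the dipstick list.
2. In SAP 9.9, add calcium/creatinine to the description of the urine collection.
3. In SAP 9.9, summarize value and change from the Day -1 baseline for urine calcium, phosphorus, creatinine and calcium/creatinine, by cohort and relative time to dose, with the 48-hour points included. Keep the listing.

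The cost is a few lines of SAP text and one small set of tables. No new samples or visits are needed.

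Optional, and not corrections: a Screening-to-end-of-treatment table of new or worsened renal ultrasound and eye findings, and a phosphorus/creatinine ratio, which neither Table 7 nor the SAP names.

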9.4.2. Safety Analyses

The primary objective of the study is to assess the safety and tolerability of ALXN1850. The endpoints to support the primary objective include incidence of TEAEs and treatment-emergent serious adverse events (TESAEs). The incidence of TEAEs and TESAEs will be summarized by System Organ Class (SOC) and Preferred Term by administration and cohort overall, by severity, and by relationship to study intervention. Adverse events will be categorized by the type of administration being received at the date of onset (ie, IV or SC). Treatment-emergent AEs and TESAEs resulting in withdrawal from the study will be listed. Participants having multiple AEs within a category (eg, overall, SOC, Preferred Term) will be counted once in that category. For severity tables, a participant's most severe event within a category will be counted. Adverse events of special interest will be analyzed similarly.

Changes from baseline in vital signs and laboratory assessments (as displayed in Table 7) will be summarized by visit for each cohort. Laboratory parameter values will be graded based on the National Cancer Institute CTCAE grading for severity (v5.0, published 27 Nov 2017). Shift tables by treatment group will be produced for these laboratory parameters. These tables will summarize the number of participants with each baseline grade relative to the normal ranges and changes to the worst highest grade assessed postdose during the study.

Electrocardiogram parameters will be measured at the specified time points, including heart rate, PR, RR, QRS, QT, and QTcF intervals. The average of the triplicate ECG readings at the time points collected will be calculated, and changes from pretreatment baseline values will be assessed.

An outlier analysis will be performed that will summarize the frequency and percentage of participants who meet any of the following outlier criteria at each visit.

- QT, QTcF interval > 450 msec
- QT, QTcF interval > 480 msec
- QT, QTcF interval > 500 msec
- QT, QTcF interval increases from baseline > 30 msec
- QT, QTcF interval increases from baseline > 60 msec

Physical examination results will be classified as Normal, Abnormal Not Clinically Significant (NCS), Abnormal Clinically Significant (CS), and Not Examined. The results will be summarized by visit for each administration.

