Summary statistics and change from baseline for chemistry, hematology, coagulation, and urinalysis will be presented by relative time to dose. Laboratory parameter values will be graded based on the National Cancer Institute CTCAE (v5.0, published 27 Nov 2017) grading for severity. Shift tables will be produced for chemistry, hematology, coagulation, and urinalysis. Shift from baseline grade tables will be presented by relative time to dose. Shift from baseline to post-baseline worst highest grade will be presented.

All clinical laboratory tests (including chemistry, hematology, coagulation, and urinalysis) will be presented in data listings.

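### End-of-treatment laboratory results are left out of the SAP's by-time summary, change-from-baseline and shift tables

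*SAP*

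**What the plan says.** Protocol 1.3 (Tables 1 and 2) schedules hematology, chemistry, coagulation and urinalysis at EoT. The collection table in SAP 9.2 agrees, with entries "Day 65/EoT (6 weeks post SC dose 3" for the first participant in a cohort and "Day 57/EoT (5 weeks post SC dose 3" for subsequent participants.

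SAP 9.2 then lists the times, relative to dose, at which results will be summarized. The list starts at baseline and closes with "24 hours post SC dose 3, and 1 week post SC dose 3". Two sets of tables are tied to it: "Summary statistics and change from baseline for chemistry, hematology, coagulation, and urinalysis will be presented by relative time to dose", and "Shift from baseline grade tables will be presented by relative time to dose".

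Two outputs are not tied to it: "Shift from baseline to post-baseline worst highest grade will be presented", and "All clinical laboratory tests (including chemistry, hematology, coagulation, and urinalysis) will be presented in data listings".

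Protocol 9.4.2 states the commitment more broadly: changes from baseline in vital signs and "laboratory assessments (as displayed in Table 7) will be summarized by visit for each cohort". SAP Section 4 keeps only unscheduled results out of the summary tables, and EoT laboratory tests are scheduled.

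**The concern.** A programmer who follows SAP 9.2 would build the laboratory tables without an EoT row. EoT is the only laboratory assessment well after dosing has ended, so it is the one visit that can show whether a change seen during dosing has persisted or resolved. Protocol 10.9 (Amendment 4) explains that EoT was chosen as the last critical PK/PD visit, at about 5.5 half-lives, and as sufficient for safety follow-up. Safety and tolerability are the primary objective.

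The omission also reaches the exploratory objective. Ionized calcium, phosphorus and magnesium are endpoints to be followed over time (SAP Section 2, Table 1). Protocol 9.4.3.4 promises graphs of them, but SAP Section 12 covers only PTH, PA, sCTX, P1NP and osteocalcin. Within the SAP, the chemistry tables of 9.2 are therefore the only by-time summaries of these three analytes, and they stop one week after the last dose.

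**Working it through.** No test or sample-size figure is involved. The check compares scheduled visits with listed summary times, and then works out the EoT label.

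**Step 1: scheduled post-baseline laboratory visits against the list** (days from Protocol 1.3 and the SAP 9.2 collection table)

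| Time relative to dose | First participant | Subsequent participants | In SAP 9.2 list |
|---|---|---|---|
| 24 h after IV | Day 2 | Day 2 | yes |
| 1 week after IV | Day 8 | Day 7 | yes |
| 2 weeks after IV | Day 14 | not scheduled | yes |
| 24 h after SC 1 | Day 16 | Day 9 | yes |
| 1 week after SC 1 | Day 21 | Day 14 | yes |
| 24 h after SC 2 | Day 23 | Day 16 | yes |
| 1 week after SC 2 | Day 28 | Day 21 | yes |
| 24 h after SC 3 | Day 30 | Day 23 | yes |
| 1 week after SC 3 | Day 36 | Day 29 | yes |
| EoT | Day 65 | Day 57 | **no** |

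There are 10 scheduled visits for first participants and 9 for subsequent ones. The list has 9 post-baseline entries. EoT is the only scheduled visit missing from it, in both schedules.

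**Step 2: time since the last dose.** SC dose 3 is given on Day 29 (first) or Day 22 (subsequent). Weeks = (visit day − dose day) / 7.

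- Last summarized visit: (36 − 29)/7 = 1.0 and (29 − 22)/7 = 1.0.
- EoT, first: (65 − 29)/7 = 36/7 = 5.1; with the −3/+7 day window, 33/7 = 4.7 to 43/7 = 6.1.
- EoT, subsequent: (57 − 22)/7 = 35/7 = 5.0; with the window, 32/7 = 4.6 to 42/7 = 6.0.

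The two EoT visits differ by one day relative to the last dose, yet SAP 9.2 labels them 6 and 5 weeks. SAP 8.2 and 9.3 call Day 65 5 weeks, which fits the 36 days. The SAP already tolerates a one-day difference: Day 51 (51 − 29 = 22 days) and Day 43 (43 − 22 = 21 days) share a 3-week label.

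**Step 3: what other sections do.** The summary lists for vital signs (SAP 9.3), PD (Section 10), immunogenicity (Section 11) and bone biomarkers (Section 12) all include 5 and 8 weeks after SC dose 3. The ECG list (SAP 9.5) goes from 1 week to 8 weeks, omitting the EoT visit when an ECG is taken and naming a time when none is scheduled. Amendment 4 moved ECGs and safety laboratory tests from the end-of-study visit to EoT. The pattern fits lists that were not updated after that move, although the documents do not say so.

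**Step 4: what still captures EoT values.** Protocol 9.4.2 defines the worst-grade shift over all postdose assessments in the study, so EoT results feed it. That table carries no time point: a participant at Grade 2 one week after the last dose falls in the same cell whether EoT is normal or still Grade 2. The listings show every value but summarize none.

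**The case against.** A reader might infer that EoT laboratory data are never summarized and that a late safety signal could go unseen. The documents do not support that, for four reasons.

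- EoT values enter the worst post-baseline grade shift, and all values are listed. With about 5 participants per cohort, each person's EoT value can be read against baseline and the earlier visits.
- Ectopic calcification, a named risk in Protocol 2.3.1, is examined directly at EoT by renal ultrasound and ophthalmological examination (Protocol 8.2.8 and 8.2.9).
- Laboratory abnormalities judged clinically significant are repeated and recorded as adverse events (Protocol 8.2.4 and 10.3.1), and TEAEs are counted to the final follow-up visit (SAP 9.1).
- PPi, PLP and the bone markers are summarized at 5 and 8 weeks.

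All of this stands and limits the consequence. None of it supplies the by-visit summary that the protocol promises.

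It can also be said that the list is introduced as what the summaries include, not as a closed set, and that SAP Section 4 excludes only unscheduled results. That supports reading the gap as a drafting slip and not as a decision to drop EoT. It does not remove the gap, because every other scheduled laboratory time is named and the list is the only specification for these tables.

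Finally, a reader might take the 6-week label as already splitting a table. It does not: no laboratory table has an EoT row, so the label currently affects no output. It would matter only once the row is added.

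**Conclusion.** The point holds in a limited form. EoT laboratory results are missing from the by-time descriptive, change-from-baseline and by-time shift tables for all of about 15 participants, contrary to Protocol 9.4.2. The loss is 1 of 10 post-baseline visits for first participants and 1 of 9 for the rest, but it is the only visit more than 7 days after the last dose. It also takes away the SAP's only late by-time summary of ionized calcium, phosphorus and magnesium. EoT data remain in the worst-grade shift and the listings, which give no by-time summary of persistence or recovery.

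The study plans no hypotheses and these tables are descriptive, so no test or decision rule changes. The conclusion assumes that the tables will be programmed from the SAP 9.2 list as written. If the table shells already carry an EoT row, only the SAP text needs correcting.

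**What to change.** In SAP 9.2, add one entry to the relative-time list, *EoT (5 weeks post SC dose 3)*, for both participant types, and carry it into the by-time shift tables. The list then has 10 post-baseline entries and covers 10 of 10 scheduled visits for first participants and 9 of 9 for subsequent ones.

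In the SAP 9.2 collection table, change the Day 65 label from 6 weeks to 5 weeks, as in SAP 8.2 and 9.3, so that first and subsequent participants fall in the same row. The ECG table in SAP 9.5 has the same 6-week label and can be aligned in the same edit.

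The cost is a wording change and one row per table. No new data, visits or protocol amendment are needed.
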